6.1 Study Intervention(s) Administered

Table 3 Study Intervention Administered During the Study

Intervention name	Dysport	Botox	Xeomin
Type	Biologic	Biologic	Biologic
Dose formulation	Lyophilised powder	Lyophilised powder	Lyophilised powder
Unit dose strength(s)	300 U/vial	50 U/vial	50 U/vial
Dosage Level(s)	40 U	16 U	16 U
Dose Frequency	Single administration on Day 1	Single administration on Day 1	Single administration on Day 1
Route of administration	Intramuscular injection	Intramuscular injection	Intramuscular injection
Use	Active-comparator	Active-comparator	Active comparator
IMP and AMP/NIMP	IMP	IMP	IMP
Sourcing	Provided by the sponsor	Provided by the sponsor	Provided by the sponsor
Packaging and labelling	Commercial product will be used. Study intervention will be provided in packs of 1 vial, labelled on primary and secondary packaging for clinical study purpose.	Commercial product will be used. Study intervention will be provided in packs of 1 vial, labelled on primary and secondary packaging for clinical study purpose	Commercial product will be used. Study intervention will be provided in packs of 1 vial, labelled on primary and secondary packaging for clinical study purpose.
Storage requirements	To be stored between 2°C and 8°C	To be stored between 2°C and 8°C	Room temperature (below 25°C)

AMP=auxiliary medicinal product; IMP=investigational medicinal product; NIMP=non-investigational medicinal product; U=units

6.2 Preparation/Handling/Storage/Accountability

1. The investigator or designee must confirm appropriate temperature conditions have been maintained during transit for all study intervention received and any discrepancies are reported and resolved before use of the study intervention.
2. Only participants screened in the study and who meet the eligibility criteria may receive study intervention and only authorised site staff may supply or administer study intervention. All study intervention must be stored in a secure, environmentally controlled and monitored (manual or automated) area in accordance with the labelled storage conditions with access limited to the investigator and authorised site staff.
3. The investigator, institution or the head of the medical institution (where applicable) is responsible for study intervention accountability, reconciliation, and record maintenance (i.e. receipt, reconciliation and final disposition records).
4. Further guidance and information for the preparation and management of the study intervention are provided in the “IMP handling manual”.
5. The sponsor will provide guidance on the destruction of unused study intervention. If destruction is authorised to take place at the investigational site, the investigator must ensure that the materials are destroyed in compliance with applicable environmental

regulations, institutional policy and any special instructions provided by the sponsor. All destruction must be adequately documented.

6.2.1 Investigational Medicinal Product Preparation

The investigator or an approved representative (e.g. pharmacist) will ensure that all IMPs are reconstituted by an independent reconstitutor (unblinded study staff) and dispensed by qualified staff members. Detailed instructions for storage, reconstitution and preparation before treatment administration will be provided in the “IMP handling manual” or similar documentation.

The vial of Dysport will be reconstituted using sterile 0.9% sodium chloride solution for injection to a concentration of 200 U/mL for administration of a dose of 40 U in 0.2 mL.

The vials of Botox and Xeomin will be reconstituted using sterile 0.9% sodium chloride solution for injection to a concentration of 80 U/mL for administration of a dose of 16 U in 0.2 mL.

A ready to administer syringe containing the study intervention will be provided to the injection responsible delegated person in order to maintain the blinding.

6.2.2 Investigational Medicinal Product Storage and Security

The investigator or an approved representative (e.g. pharmacist) will ensure that all IMPs and any other study related material are stored in a secured area, under recommended temperature monitored storage conditions, in accordance with applicable regulatory requirements.

All study interventions must be stored as indicated in [Table 3](#). Sterile 0.9% sodium chloride solution for reconstitution can be stored at room temperature.

6.2.3 Investigational Medicinal Product Accountability

All IMPs and any other study related material are to be accounted for on the IMP accountability log provided by the sponsor. Used vials, empty or not, must be retained at site in accordance with local regulations. It is essential that unused supplies, as well as used supplies or empty boxes of used supplies, are retained for verification (by sponsor’s unblinded representative). Unused supplies, as well as used supplies or empty boxes of used supplies, will be either destroyed at the site or in the local depot. Drug accountability records will be maintained by the independent reconstitutor (unblinded study staff) documenting the subject allocated treatment number and the number of vials used and not used.

6.3 Measures to Minimize Bias: Randomisation and Blinding

6.3.1 Randomisation

The sponsor’s randomisation manager who is a statistician independent of the study will prepare the list of randomisation numbers for this study. It will be produced in blocks, on a balanced ratio [1 Dysport: 1 Botox: 1 Xeomin].

After eligibility is confirmed at Day 1, participants will be assigned a randomisation number and to the associated study intervention group, in sequential order within the centre. Each participant will be treated with the intervention allocated to this randomisation number. This will be done by an unblinded pharmacist (independent reconstitutor) in charge of the study intervention preparation, by considering the first unused treatment allocation envelope among the set of envelopes provided to the centre. The assigned randomisation number will have to be specified on the treatment kit, vial and syringe used for the study intervention reconstitution.

The investigator, the unblinded pharmacist, and investigator staff will under no circumstances change the randomisation number or the study intervention group allocated to the participant.

Recruitment will stop once 45 participants have been randomised. Randomised participants who terminate their study participation for any reason before starting intervention will retain

their randomisation number (the randomisation number will not be reused). The next participant will be assigned the next randomisation number.

Randomised participants who discontinue the study early will not be replaced.

The sponsor's randomisation manager will keep the master list of randomisation numbers. Access to this list must be restricted until authorisation is given to release it for final analysis.

6.3.2 *Maintenance of Blinding*

During the study, the sponsor, investigator (including study site personnel) and the participant will be blinded to the study intervention. To maintain the blind during the study only a qualified, trained and unblinded person independent of the injector and investigator will prepare (i.e. reconstitute) the study intervention and will have no further involvement in the study. This person will be fully trained in the method of preparing the study intervention and the importance of their role in maintaining the blind for the participant, the investigator and the rest of the team.

In the event of a quality assurance audit, the auditor(s) will be allowed to access to unblinded study intervention records at the site to verify that randomisation/dispensing has been done accurately.

Due to slight differences in colour between the study interventions and to maintain the blind during the study, the injector will also be independent from the investigator and be unblinded (note: the injector will be different from the person who will evaluate CMAP). Following injection of the study intervention, the injector will have no further involvement in the study.

Two sets of individual code break envelopes (an envelope per randomisation number) will be prepared by the sponsor's randomisation manager to enable emergency code break procedures for individual participants without compromising the blind of the study. One set will be provided to the investigational site and one set will be provided to the central department of pharmacovigilance at the sponsor.

The code break material will be retained by the investigator (or representative) in a secured area.

In case of an emergency, the investigator has the sole responsibility for determining if unblinding of a participants' intervention assignment is warranted. Participant safety must always be the first consideration in making such a determination.

If a participant's intervention assignment is unblinded, the sponsor must be notified within 24 hours after breaking the blind.

The investigator must reseal the envelope. The investigator will sign, date and provide reason for the code break on the emergency code break form and on the sealed envelope. The date and reason for identifying the intervention will be recorded in the eCRF.

Once the study is complete, all code break material (sealed and opened) must be inventoried and returned to the sponsor.

Sponsor safety staff may unblind the intervention assignment for any participant with an SAE. If the SAE requires that an expedited regulatory report be sent to one or more regulatory agencies, a copy of the report, identifying the participant's intervention assignment, may be sent to investigators in accordance with local regulations and/or sponsor policy.

6.4 Study Intervention Compliance

Participants will receive study intervention directly from the investigator or designee, under medical supervision at the study site on Day 1. Therefore, participant compliance with study intervention is not expected to be an issue. The date, time and volume of administration will be recorded in the source documents and in the eCRF. The dose of study intervention and study participant identification will be confirmed at the time of dosing by a member of the study site staff other than the person administering the study intervention.

6.5 Dose Modification

No dose modification will be required in this study.

6.6 Continued Access to Study Intervention after the End of the Study

The participants will not receive any additional study intervention following the end of the study.

6.7 Treatment of Overdose

For this study, any dose of Dysport, Botox or Xeomin greater than that defined in Section [6.1](#) will be considered an overdose.

In the event of an overdose, the investigator should:

- Contact the medical monitor immediately.
- Closely monitor the participant signs and/or symptoms of excessive muscle weakness or muscle paralysis. Note: symptoms of overdose may not present immediately following injection. Should accidental injection or ingestion occur the participant should be medically supervised for several weeks.
- Document the quantity of the excess dose, as well as the duration of the overdose. See Section [10.3.1](#) for reporting requirements concerning overdose.

6.8 Concomitant Therapy

Any prior medications/nondrug therapies used by the participant within 30 days prior to the Screening visit (and not continued during the study) or concomitant medications/nondrug therapies given during the study will be indicated on the eCRF. Dose and generic name or trade name will be indicated.

The investigator will be advised not to use any dermal topics (including anaesthetic topics) on the participant prior to the injection of study intervention on Day 1. In addition, the following concomitant medications are not permitted during this study:

- Any form of BoNT (other than the specific study intervention) for administration into any site of the body.
- Any experimental new drug or device.
- Medications that affect neuromuscular transmission, such as curare-like non-depolarising agents, lincosamides, polymyxins, anticholinesterases and aminoglycoside antibiotics, within the past 30 days of Baseline and during the study.
- Medications that affect bleeding disorders (antiplatelet agents and/or anticoagulants given for treatment or prevention of cardiovascular /cerebrovascular diseases).
- Concomitant medications for other purposes are allowed at the investigator's discretion. It is recommended that the dosage for these medications is kept constant throughout the study. Where medically appropriate, all concomitant medications being taken by a participant at entry into the study should continue at the same dose.

Concomitant use of anticholinergic drugs (which may potentiate systemic anticholinergic effects) is permitted if the dosage has been stable for the 6 weeks prior to study intervention and is expected to remain at this stable dose throughout the study.

Concomitant use of any vaccine against COVID-19 is permitted from 7 days after injection of study intervention. COVID-19 vaccination dates should not be delayed to enable study participation. Participants who are unable to adhere to the COVID-19 vaccination guidance outlined in this protocol should not be included in the study (also see Section [5.2](#)).

7 DISCONTINUATION OF STUDY INTERVENTION AND PARTICIPANT DISCONTINUATION/WITHDRAWAL

7.1 Discontinuation of Study Intervention

In this study, there will be only one treatment cycle administered on Day 1 of the study, thus discontinuation of the study intervention is not applicable. In the event, a participant is randomised, but does not receive study intervention, the participant will not remain in the study and the EoS/EW assessments will not be performed

7.1.1 *Temporary Discontinuation*

In case of suspected or confirmed COVID-19 (SARS-CoV-2) infection at the Baseline visit (Day 1), the study intervention administration may be temporarily postponed depending on the participant's clinical presentation. In some cases, the investigator may request a participant be retested before the intervention administration is administered.

In the event of suspected or confirmed COVID-19 infection after study intervention administration on Day 1, the participant will be required to isolate for at least 14 days and have a negative SARS-CoV-2 test before returning to the study site for the next follow-up visit. A participant may be permanently discontinued at the discretion of the investigator if further study participation is deemed to be harmful for the participant, or other participants in the study and/or study site personnel.

7.2 Participant Discontinuation/Withdrawal from the Study

- A participant may withdraw from the study at any time at his own request or may be withdrawn at any time at the discretion of the investigator for safety, behavioural or compliance reasons.
- At the time of discontinuing from the study, if possible, an early withdrawal visit should be conducted, as shown in the SoA. See SoA for data to be collected at the time of study discontinuation and follow-up and for any further evaluations that need to be completed.
- The reason for discontinuation will be recorded in the eCRF.
- If the participant withdraws consent for disclosure of future information, the sponsor may retain and continue to use any data collected before such withdrawal of consent.
- If the participant withdraws consent, it should be explained in detail in the medical records by the investigator as to whether the withdrawal is only from further receipt of study intervention or also from study procedures and/or posttreatment study follow-up. This information must be entered in the eCRF.
- If a participant withdraws from the study, he may request destruction of any samples taken and not tested, and the investigator must document this in the site study records.

A participant may discontinue participation in the study at any time for any reason (e.g. lack of efficacy, withdrawal of consent, adverse event (AE)). The investigator and/or sponsor can withdraw a participant from the study at any time for any reason (e.g. protocol violation or deviation noncompliance with the protocol conditions or AEs). All cases of discontinuation will be discussed between the investigator and the sponsor.

If a participant decides to withdraw from the study after administration of IMP, or should the investigator decide to withdraw the participant, all efforts will be made to complete and report the observations up to the time of withdrawal as thoroughly as possible. A complete final evaluation at the time of the participant's withdrawal should be made and an explanation given of why the participant is withdrawing or being withdrawn from the study.

The reason for and date of withdrawal from the study must be recorded on the electronic case report (eCRF). If a participant withdraws consent, every attempt will be made to determine the reason. If the reason for withdrawal is an AE or a clinically significant laboratory test abnormality, monitoring will continue until the event has resolved or stabilised, until the participant is referred to the care of a local health care professional, or until a determination of a cause unrelated to the IMP or study procedure is made. The specific AE or test result(s) must be recorded on the eCRF. All evaluations should be performed, according to the protocol, on the last day the participant receives IMP, or as soon as possible thereafter

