5.7.1.2 Handling of Dropouts and missing data

Diligent attempts will be made to limit the amount of missing data and to follow-up all randomised participants to collect the primary and secondary pharmacodynamic endpoints for the statistical analysis.

The Mixed Model for Repeated Measures (MMRM) is implicitly handling missing data as Missing At Random (MAR) without explicit imputation. This missingness assumption appears meaningful given the long term pharmacodynamic effect of the investigated compounds: the effect of the drug will persist after discontinuation and is not expected, given baseline profile of the participant and assessments until the timepoint of discontinuation, to depend on whether the participant remains observable in the study or drops out.

In case of occurrence of a major PDs with the potential to interfere with CMAP total amplitude (see [Section 5.3](#)), CMAP data collected after the PDs will be ignored, and will be handled by the model as MAR. This implements a 'per protocol' analysis assessing the treatment difference occurring in case participants adhere to the protocol by using a hypothetical handling strategy for this ICE.

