5.7.2 Analysis of Primary Pharmacodynamic Endpoint

5.7.2.1 Endpoint, Treatment Effect and Estimand Definition

To assess the primary objective, the primary estimand has the following key attributes:

- Population of interest: healthy adult male participants as defined by the listed inclusion/exclusion criteria in Section 5.1 and 5.2 of the protocol.
- Variable/endpoint of interest: CMAP total amplitude at Week 28, measured as percentage relative to baseline (%), calculated as [value at Week 28 (mean of the three measurements/baseline value (means of the six measurements)]*100.

- ICEs are the following:
 - a) Study discontinuation
 - b1) PDs with potential impact on relevant CMAP total amplitude assessments (i.e. participant received the wrong study intervention and CMAP at Week 28 performed out of a specified time window ($> +/- 2$ weeks))
 - b2) PDs with no expected impact on relevant CMAP assessments (e.g. other time window violations, PDs related to covid-19)
- Treatment regimen: Dysport, Botox or Xeomin will be administered as described in Section 6 of the protocol and potential intake of permitted concomitant medications (for a list see Section 6.8 of the protocol).
- Population-level summary of the treatment effect of interest: the difference in average percentage relative to baseline in each study intervention group in CMAP total amplitude at the respective timepoint.

For ICEs (a) and (b1) a hypothetical strategy will be used, the treatment difference which would have been measured if the ICE would not have happened is of interest and will be assessed taking into account the long term pharmacodynamic effect of the investigated compounds. This implies that assessments after the occurrence of a major protocol deviation interfering with CMAP total amplitude will be ignored for the primary analysis. No imputation of missing CMAP will be done (MMRM analysis, please refer to [section 5.7.1.2](#)). For ICEs (b2), a treatment policy will be used.

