5.7.2.4 Supplementary Analysis

In case of occurrence of major PDs with the potential to interfere with CMAP total amplitude ([see section 5.3](#)), a supplementary analysis using the same MMRM model used for the primary analysis will be conducted using a treatment policy strategy to handle this ICE. All collected CMAP data will be taken into account in this supplementary analysis, even when occurring after PDs.

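### Protocol 7.2 lets a dosed participant be withdrawn for a deviation or noncompliance alone, which ends CMAP follow-up that the SAP's own estimand would use

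*Protocol*

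**What the plan says.** Protocol 7.2 states the withdrawal rule twice. A participant "may be withdrawn at any time at the discretion of the investigator for safety, behavioural or compliance reasons". Later: "The investigator and/or sponsor can withdraw a participant from the study at any time for any reason (e.g. protocol violation or deviation", with noncompliance and adverse events also given as examples. Neither statement separates participants who have been dosed from those who have not. After withdrawal the protocol plans an early-withdrawal visit if possible, and "all efforts will be made to complete and report the observations up to the time of withdrawal as thoroughly as possible". The Schedule of Activities includes CMAP at that visit.

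Protocol 7.1 notes that there is a single treatment on Day 1, "thus discontinuation of the study intervention is not applicable". Protocol 6.3.1 adds: "Randomised participants who discontinue the study early will not be replaced".

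The SAP takes a different line on follow-up. Section 5.7.1.2 says: "Diligent attempts will be made to limit the amount of missing data and to follow-up all randomised participants". Section 5.7.2.1 divides protocol deviations in two. Those that may affect CMAP (b1: wrong intervention, or Week 28 CMAP more than 2 weeks out of window) get a hypothetical strategy. For those with no expected effect, "For ICEs (b2), a treatment policy will be used". Section 5.7.2.4 adds a treatment-policy supplementary analysis for interfering deviations: "All collected CMAP data will be taken into account in this supplementary analysis, even when occurring after PDs". Section 5.7.2.3 plans no sensitivity analysis.

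**The concern.** In a trial with repeated dosing, withdrawing a noncompliant participant may at least stop treatment. Here there is nothing left to stop, so a withdrawal for compliance or a deviation can only end observation. Protocol 9.4.2.4 itself says that the drug effect persists after discontinuation, so CMAP recorded later would still be informative.

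Three things are at stake. First, a deviation that the primary estimand handles with observed data becomes a study discontinuation, handled by the model under missing at random. Second, the recovery endpoints can be filled by imputation where a measurement could have been taken. Third, these losses are made by discretion and are avoidable, in a trial of 15 per arm with no replacement and no allowance for loss after randomisation.

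**Working it through.** **How the passages act on one participant**

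Take a dosed participant with a deviation at Week 12 that is not expected to affect CMAP (b2; the SAP's examples are other window violations and COVID-19-related deviations).

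- *If he stays:* his Week 28 CMAP enters the primary MMRM as observed, by treatment policy. His recovery status at Weeks 28 and 40 is measured.
- *If he is withdrawn under 7.2:* the event is now study discontinuation (ICE a). His visits to Week 12 and any early-withdrawal CMAP remain, but the Week 28 and Week 40 values are missing and are handled under missing at random. Under SAP 5.7.3.1, recovery is set to no recovery only if the next available CMAP is below 85% of baseline. With no CMAP after the event it is set to recovery. The SAP does not say whether the early-withdrawal CMAP counts as being after the event. An imputed recovery in a comparator arm widens the difference in favour of Dysport; in the Dysport arm it narrows it.

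For b1 deviations the primary analysis ignores later CMAP in any case. After a wrong injection, the supplementary analysis in 5.7.2.4 would use later CMAP, and withdrawal removes it. This assumes that the participant is in the PD set, whose definition requires the appropriate dose.

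**Power**

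Inputs (Protocol 9.2): difference 18, common SD 15, 15 per arm, two-sided 5% t-test; stated power at least 88% per comparison and at least 81% for both. The only loss allowed for is 5% screening failure: 45/0.95 = 47.4, hence 48 screened. No rate of loss after randomisation is given; 0 to 2 per arm is my assumption.

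Formula: noncentrality = 18 / (15 × √(1/n₁ + 1/n₂)). Power is the probability that a noncentral t exceeds the two-sided 5% critical value in absolute size. The degrees of freedom are n₁ + n₂ − 2 for the two-arm test, or total N − 3 with the SD pooled over three arms.

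| Week 28 values in the comparison | Noncentrality | Two-arm t-test | SD pooled over three arms |
|---|---|---|---|
| 15 v 15 | 3.286 | 88.7% (df 28) | 89.4% (df 42) |
| 14 v 15 (third arm 15) | 3.229 | 87.5% (df 27) | 88.4% (df 41) |
| 14 v 14 (third arm 14) | 3.175 | 86.3% (df 26) | 87.2% (df 39) |
| 13 v 13 (third arm 13) | 3.059 | 83.5% (df 24) | 84.5% (df 36) |

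The first row reproduces the stated 88%. Simulated power to reject both nulls under Hochberg is 81.2% with 15 per arm (pairwise t-tests), which reproduces the stated 81%. It is 77.9% with 14 per arm and 73.7% with 13 per arm. With the pooled SD the three figures are 82.5%, 79.1% and 75.3%.

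All of these are complete-case figures. The MMRM recovers part of the loss from earlier visits, so they overstate the cost.

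**The case against.** The rule is permissive, and 7.2 requires every discontinuation to be discussed between investigator and sponsor. Nothing says that such removals will be common. This stands as to frequency. But a discussion sets no criterion and does not keep anyone in follow-up.

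The SAP promises only diligent attempts, and its supplementary analysis uses whatever was collected, so the conflict is one of intent rather than of strict contradiction. That is fair for those two sections. It does not answer the b2 handling, where the primary estimand calls for data after the deviation.

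Four stronger readings are tempting, and the documents do not support them:

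- *Withdrawal simply discards the participant's data.* Earlier visits and, where possible, an early-withdrawal CMAP are kept. A withdrawal after Week 28 leaves the primary value intact.
- *A participant who misses visits will be removed.* Protocol 7.3 tells the site to make contact, reschedule and counsel him.
- *The treatment-policy supplementary analysis loses its input.* One of its two triggers is a late or early CMAP, where the measurement exists by definition. The loss concerns the wrong-injection case.
- *One removal takes power below the stated 88%.* That holds for the two-arm complete-case test (87.5%), but not with the SD pooled over three arms (88.4%). Any dropout would have the same effect.

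Nor do the documents suggest removal by arm: Protocol 6.3.2 keeps sponsor and investigator blinded.

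**Conclusion.** The point holds in a limited form. Protocol 7.2 permits withdrawals after dosing that stop no treatment, and they replace observed Week 28 and Week 40 CMAP with reliance on missing at random, with no sensitivity analysis. It is out of step with the SAP's follow-up aim and with its treatment-policy handling of b2 deviations. It can also turn a measurable recovery outcome into an imputed one.

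The size cannot be fixed from the documents, since no rate of such removals is given. On the assumed 0 to 2 losses per arm, the power cost is about 1 point for a single loss and about 5 points for two in every arm (88.7 − 83.5 = 5.2; pooled, 89.4 − 84.5 = 4.9), before any recovery by the MMRM. The reason to act is to avoid discretionary missing data; power is secondary. The change is worth making because it costs so little.

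**What to change.** Reword 7.2 so that the general power to withdraw at any time is itself limited. After dosing, a protocol deviation or noncompliance alone should not be a ground for withdrawal by the investigator or sponsor. Deleting the examples would not be enough, because the any-reason wording would remain and contradict the new sentence.

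Add that such a participant stays in the scheduled CMAP visits, or at minimum attends Week 28 and Week 40 if he consents, and that the deviation is recorded and handled as the intercurrent event the SAP defines. The reduced schedule protects the primary and key secondary timepoints but gives less information on time to recovery and duration of response.

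Leave unchanged withdrawal at the participant's own request, withdrawal for safety, and withdrawal where continued participation could harm him, other participants or staff (the last is foreseen in 7.1.1). For that reason behavioural grounds should not be struck out wholesale.

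Cost: wording in one protocol section, with no new visits or procedures. Downside: the site goes on following a few less compliant volunteers.
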